### **8.1. Adverse Events and Deaths**

#### **8.1.1. AE Definitions**

The following AEs are recorded on eCRFs:

- All SAEs
- All AEs attributed to doxycycline in the opinion of the site investigator

#### **8.1.2. Adverse Event Summary Tables**

The number of SAEs will be tabulated by grade and arm. For the dPEP arm, related AEs will be tabulated by grade (see below of definition of relatedness).

#### **8.1.3. Listings of Serious Adverse Events (SAE), Adverse Event Dropouts, and Death**

SAE data will be reported by related and not related.

Participant data listing for SAEs will be by grade and arm, sorted by reported date within participant. Unique information included in the listing contains SAE onset and resolution dates and times; verbatim description of SAE; relationship to study medication, action taken, and outcome.

Participant data listing for related AEs will be by grade, sorted by reported date within participant. Unique information included in the listing contains AE onset and resolution dates and times; verbatim description of AE; action taken, and outcome.

A listing will present participants who discontinue study drug in the dPEP arm due to an adverse event, and the reasons for discontinuations:

- Requirement for prohibited concomitant medications or other contraindication to doxycycline
- Pregnancy
- Occurrence of an adverse event requiring discontinuation of doxycycline
- Request by participant to terminate study treatment
- Clinical reasons believed life threatening by the physician, even if not addressed in the toxicity section of the protocol
- Requirement for chronic tetracycline use ( $\geq 14$  days)

## **8.2. PrEP use**

### **Tabulation of time on PrEP**

Tabulations of PrEP will use the following assessments:

- Residual hair samples of participants will be tested for quantitative tenofovir drug levels to measure monthly use of tenofovir disoproxil fumarate/lamivudine PrEP.
- Reported time on PrEP prior to enrollment
- Tabulation of PrEP use at each visits
  - Self-report of PrEP adherence (How well have you taken PrEP in the past month? How often do you take PrEP?)
  - PrEP dispensing (PrEP discontinued prior to visit or on PrEP prior to the visit. Has PrEP/PrEP dispensed)

## **8.3. Tolerability**

Tolerability is assessed for participants on the dPEP arm through

- a self-reported response to whether a participant did not take dPEP because of side-effects.

Descriptive: The Yes/No responses of dPEP side effects will be tabulated for each study visit among dPEP participants

- Symptoms from the side-effect questionnaire

Descriptive: Symptoms, collected at each visit, will be tabulated for each arm

## **8.4. Acceptability**

Acceptability is assessed in the dPEP arm only via a 7 question acceptability questionnaire using a 5 point Likert scale.

Descriptive: The scales will be converted to an acceptability score, the dPEP Acceptability and Optimism CRF, (using reverse coding where appropriate), and summarized by visit. Individual questions will also be reported in detail. This will be supplemented with qualitative interviews for a mixed methods analysis.

## **8.5. Adherence**

Adherence is assessed as coverage of sex acts for this event-driven dosing and may have impact on effectiveness of medication.

### **8.5.1. Coverage of sex acts**

Assessed in the dPEP arm only:

## Measures

- Last 14 days (up to 3 days prior to visit) calendar reporting of days taking dPEP and days with sex.
- SMS: Self-reported coverage of last week: last 7 days # days with “dance” (SMS term used to mean sex), and # days taking dPEP.

Definition: Acceptable coverage for a participant is defined as on 80% of days with sex, the participant self-reports use of dPEP within 72 hours.

### Descriptive:

EchoMobile SMS data: Past-week use of dPEP by reported sex acts among dPEP study arm participants in a table over all follow-up time, excluding periods where participant is on a documented study drug hold.

Timeline follow-back calendar: Past 2-week (day -14 to -3) participant-reported dPEP coverage among those with reported sex, by scheduled visit and over all follow-up time, excluding visits where participant is on a documented study drug hold.

### **8.5.2. Longitudinal adherence-effectiveness analysis:**

Hair samples collected at quarterly follow-up study visits for all treatment group participants will be analyzed for quantitative hair drug levels. Based on HIV PrEP studies, we assume that dPEP will either be used regularly or not at all and that underdosing will be a rare occurrence. Because quantifying doxycycline drug hair levels is not yet standardized, we will not describe true event-based adherence but rather use vs. non-use.

1. Doxycycline use (defined as detectable doxycycline in a hair sample – binary variable) will be analyzed using GEE to measure effect of dPEP use compared to nonuse in preventing STI cases (quarterly measure of any incident STI – binary variable).

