**Adherence:** All participants will receive 1:1 adherence counselling for PrEP with individualized barrier identification and problem-solving assistance. Participants in the dPEP arm will receive 1:1 adherence counselling as well as reminders on their daily PrEP tablet bottle as a reminder to assess personal need for dPEP on that day. A number of measures will be used to determine adherence:

**Self-reported measures:** Sexual behavior and, for those assigned to the dPEP arm, pill-taking behavior, will be measured by timeline follow-back calendar at each follow-up visit to assess exposures and dPEP use. Because dPEP is an exposure-driven medication, adherence is dependent on use of dPEP following each exposure.

**Real-time behavioral measurement (optional):** Weekly SMS will be sent in English, *KiSwahili* or *DhoLuo* as part of a momentary ecological assessment of adherence and exposure. Exposure (i.e., condomless sex) will be referred to by a code word for added privacy: for example, "How many times did you dance [have sex without a condom] this week?" [If in the dPEP arm] "How many times did you take dPEP this week?" We have used real-time SMS data collection in multiple prior PrEP studies in Kenya; cell phones are very common in Kenya (outnumbering citizens). Encrypted transmission, password protection to open the surveys, and immediate deletion permit sensitive data to be collected safely. Studies of PrEP demonstrated that there was improved comfort with reporting sexual behavior via SMS, though objective adherence measures were far superior to self-report.

**Objective measures:** Hair drug levels will be measured to more objectively assess quantitative exposures to dPEP, for several analyses. Hair samples (50-100 strands) will be collected following consent to collection and confirmed eligibility for hair collection (occipital hair >0.5cm in length with absence of bleaching) from all participants at each visit (Months 0/3/6/9/12). Hair samples will be shipped to [name] UCSF Hair Analytical Laboratory (HAL).

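### SAP 8.5.2 counts any detectable hair doxycycline as use, so its use-versus-non-use estimate mixes low and high coverage of exposures and may be distorted; no SAP model relates STI to coverage

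*SAP*

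**What the plan says.** SAP 8.5.2 covers hair samples from dPEP-arm participants. Citing HIV PrEP studies, it says that "we assume that dPEP will either be used regularly or not at all and that underdosing will be a rare occurrence". Because hair quantification is not standardized, it adds that "we will not describe true event-based adherence but rather use vs. non-use". Item 1 codes use as "defined as detectable doxycycline in a hair sample" and fits a GEE against any incident STI in the quarter, to "measure effect of dPEP use compared to nonuse in preventing STI cases". No covariates and no restriction to sexually exposed women are stated.

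Elsewhere adherence is graded. The protocol's Adherence text states: "Because dPEP is an exposure-driven medication, adherence is dependent on use of dPEP following each exposure". Protocol section 10.0, under secondary outcomes, measures it as a percentage of condomless episodes followed by dPEP. SAP 8.5 opens: "Adherence is assessed as coverage of sex acts for this event-driven dosing and may have impact on effectiveness of medication". SAP 8.5.1 sets a threshold: "Acceptable coverage for a participant is defined as on 80% of days with sex", with dPEP reported within 72 hours. The SAP plans only descriptive summaries of this coverage measure.

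**The concern.** HIV PrEP in this trial is a daily tablet, so an all-or-none pattern may be reasonable there. dPEP is taken after exposures, and a woman can cover some and miss others. An 80% threshold has a purpose only if partial coverage is expected.

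If one dose in the hair window is detectable (the documents do not say), a woman who covered one exposure in eight falls in the same group as a woman who covered all eight. A weak item 1 result could then mean that the drug protects poorly or that it was taken after too few exposures. These have different consequences for policy. The protocol's Adherence paragraph in section 10.0 lists the relationship between adherence and STI protection as a purpose of the hair data, so the question matters to the trial.

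The reference group has a separate problem. A woman with no sex has no reason to take dPEP and little risk of STI, yet item 1 places her with women who had sex and took nothing.

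**Working it through.** **1. The plan's own figure.** SAP 8.5.2 states no number. The relevant figure is the event count in SAP 3.3.1. With 446 women and 10% loss, 446 × 0.9 / 2 = 200.7 per arm. Then 200.7 × 0.22 = 44.2 and 200.7 × 0.11 = 22.1, which reproduces the stated 44 and 22. An adherence model in the dPEP arm therefore has about 22 first events, plus any repeat infections.

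**2. Pooling of coverage levels, equal exposure.** Let E be the risk reduction at full coverage, s the share of detected samples from low-coverage women, and c their coverage. Assume that protection is proportional to coverage and that exposure is equal in all groups. Then

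RR(detected vs not) = 1 − E × [1 − s × (1 − c)].

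The values of s and c are assumptions; no document gives them. E = 0.50 is set equal to the planned trial effect. E = 0.70 is the chlamydia reduction that the protocol cites from the French MSM trial.

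| s | E=0.50, c=20% | E=0.50, c=50% | E=0.70, c=20% |
|---|---|---|---|
| 5% | 0.52 | 0.51 | 0.33 |
| 10% | 0.54 | 0.53 | 0.36 |
| 20% | 0.58 | 0.55 | 0.41 |
| 30% | 0.62 | 0.58 | 0.47 |
| 50% | 0.70 | 0.63 | 0.58 |

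The undiluted values are 0.50, 0.50 and 0.30. At s = 5% the shift is at most about 0.03.

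**3. Unequal exposure.** Let low-coverage women have m times the exposures of the others, with risk proportional to exposure. With E = 0.50, s = 30%, c = 20%:

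RR = 0.7 × 0.50 + 0.3 × m × (1 − 0.50 × 0.20) = 0.35 + 0.27m.

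This gives 0.42 at m = 0.25, 0.49 at 0.5, 0.62 at 1 and 0.89 at 2. The first two lie below 0.50, so distortion can also exaggerate protection.

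**4. No sex counted as non-use.** Let a share u of undetected intervals come from women with no sex and zero STI risk, with no partial users at all. Then RR = 0.50 / (1 − u), which is 0.56, 0.63, 0.71 and 1.00 for u = 10%, 20%, 30% and 50%. SAP 9.2 excludes women with no reported exposure in the last month when it counts non-use. SAP 8.5.2 does not.

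**5. What else in the plan relates adherence to STI.**
- SAP 7.5.3 (per protocol) censors the dPEP arm at the first documented discontinuation of more than 2 weeks. It does not measure coverage.
- SAP 8.5.1 tabulates calendar coverage by visit, without STI outcome.
- SAP 8.5.2 item 2 sets hair tertiles against SMS-reported doses, without STI outcome.
- SAP 8.5.2 item 3 compares mean hair concentration at visits with and without an incident STI. Concentration follows doses taken, not the share of exposures covered; a woman with few exposures, all covered, may have a low level.
- The Acceptability paragraph of protocol section 10.0 names dPEP adherence and STI outcomes in a GEE, set against facilitators and barriers. The SAP carries forward no model of STI on coverage.

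**6. Windows.** The calendar covers day −14 to −3, which is 12 days. The hair window in item 2 runs from 5 weeks to 1 week before the visit, day −35 to −7. They share about one week, and the STI outcome covers a quarter.

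**The case against.** SAP 8.5.2 says openly that it studies use against non-use, and why. For that estimand, mixing levels of use is not a bias in itself. This stands: the difficulty arises when the estimate is read as protection under proper use, which the all-or-none sentence invites.

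A reader might infer that the estimate is certainly diluted. The documents do not support this. They give no share of partial users, no exposure by group and no detection limit in doses. If underdosing is as rare as assumed, the shift from pooling is negligible, and unequal exposure can reverse it.

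A reader might also infer that item 1 is the only model of effect on drug, or that the assumption is never checked. Neither is right. SAP 7.5.3 is an on-drug model, and the coverage tables and graded hair summaries will give some indication of how common partial use is. The gap is narrower: no regression of STI on coverage.

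Finally, one could propose to replace the hair variable by a hair-by-coverage split. The case against is sound. It would divide an objective measure by self-report, although the protocol reports that objective measures did much better in earlier PrEP studies. The windows overlap by only about a week, and with a no-sex category about 22 first events would spread over four cells. Coverage should be modelled beside the hair contrast, not inside it.

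**Conclusion.** The concern holds in conditional form. The all-or-none assumption conflicts with the documents' own event-driven, graded definition of adherence. Item 1 as written pools coverage levels and counts unexposed women as non-users, and no SAP model of STI on coverage fills the gap.

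The size is unknown. Pooling alone moves an RR of 0.50 to between 0.52 and 0.70 in the illustration at 20% coverage. That rests on proportional protection, equal exposure and an assumed 5% to 50% of partial users. With unequal exposure, one scenario spans 0.42 to 0.89, so no direction should be claimed. This is a non-randomized comparison within one arm. The ITT primary analysis does not depend on it, and the priority is minor.

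**What to change.** Change SAP 8.5.2 before database lock, as the SAP Introduction allows:

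1. Delete the all-or-none assumption.
2. Keep detected versus not detected as item 1, labelled 'any use'. Restrict it to, or stratify it by, visits with reported sexual exposure, in line with SAP 9.2.
3. Add a pre-specified GEE in the dPEP arm of quarterly any STI on calendar coverage. Use coverage as continuous and as below 80% versus at least 80%, adjusted for number of sex days. State that the 80% rule, defined for a participant, is here applied per visit.
4. As a sensitivity analysis among women who opted in to SMS, use SMS-reported coverage over the hair window. SMS gives weekly counts of sex days and dosing days, so this is a ratio and does not link doses to acts.
5. Report the share of detected samples with calendar coverage below 80%, as a direct check on the deleted assumption.

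The cost is SAP wording and derived variables from data already collected. The coverage model will be imprecise. If 22 first events split evenly between two coverage groups, the SE of the log RR is about √(1/11 + 1/11) = 0.43, so the 95% limits are the estimate divided and multiplied by exp(1.96 × 0.43) ≈ 2.3. Repeat infections would narrow this and an uneven split would widen it. Coverage remains self-reported, and its 12-day window only partly represents the hair window and the quarter. The report should say so.

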### 2.2. Study Endpoints

#### 2.2.1. Primary Efficacy Endpoints

##### Effectiveness of doxycycline

The primary endpoint is assessed using the following STI endpoints at month 3, 6, 9 and 12 visits:

- Documented positive vaginal/cervical GC
- Documented positive vaginal/cervical CT
- Early syphilis infection based on four-fold increase in non-treponemal titers.

The primary trial endpoint is any newly diagnosed STI, defined as any one of the above after the enrollment visit, with the exception of re-diagnosis of the same infection at a test of cure visit within 28 days of first treatment of a baseline or incident infections (which is considered a non-cured infection and re-treated). Any infection newly diagnosed at an interim visit will be counted as a primary endpoint for the subsequent scheduled visit i.e., if a participant is diagnosed with new GC infection at an interim visit 40 days after their 6 month visit, this will be analysed as a primary 9 month endpoint. Endpoints are reviewed by committee, blinded to study arm, and primary endpoints designated in that review.

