### **2.2.4. Adherence**

Adherence is only assessed in the dPEP arm

- Weekly SMS questions
  - Weekly questions collected in participants who opted in to SMS.
  - Number of days in the last 7 days when dPEP was taken
  - Number of days in the last 7 days when participants had sex or “danced”).
- Hair samples
  - Collected quarterly
    - Quantitative amount of doxycycline in 1cm segments from cut end to tip which corresponds with a 4-week period of dPEP use (starting 1 week ago).
- Self-report of coverage of sexual contacts in the prior 14 days to 3 days in the dPEP arm:
  - Quarterly (timeline follow-back) adherence questionnaire.

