#### Secondary analyses

2. Describe the relationship between quantitative tertials of doxycycline hair drug levels (low, medium, and high) and the number of dPEP doses reported in SMS in the 4-week time period of hair sample (5 weeks prior to study visit until 1 week prior to study visit) by generating a scatterplot and reporting the mean number of doses reported per quantitative category.
3. The mean hair drug concentration among hair samples collected at study visits when an incident STI (CT, NG, or TP, combined and per infection) was detected will be described and compared to study visits when no incident STI was detected among treatment group.

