### **9.2. Contamination and non-use:**

Hair samples were collected at all study visits. A random 10% subset of all participants at enrollment visit and 10% subset of samples from follow up study visits from the standard of care group will be analyzed for doxycycline drug concentrations to summarize instances of doxycycline detection at study enrollment (prior to dPEP initiation) or in the standard of care group. All hair samples collected in follow up study visits in the treatment group will be analyzed for instances of doxycycline non-detection, i.e., non-use (excluding participants with no sexual exposure reported in the last month). The percentage of participants with doxycycline detected in standard of care group will be compared with percentage of participants with doxycycline detected in dPEP arm over time, quarterly.

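### SAP 8.5.2 can pair an interim infection with hair exposure that falls wholly after its diagnosis, and item 1 does not say which hair segment defines use

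*SAP*

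**What the plan says.** **Exposure and outcome.** SAP 8.5.2 item 1 sets the exposure as "Doxycycline use (defined as detectable doxycycline in a hair sample – binary variable" and the outcome as "quarterly measure of any incident STI – binary variable". No segment, minimum length or look-back period is named. Item 3 compares mean hair concentration between visits with and without an incident STI.

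**When hair is taken.** "Hair samples collected at quarterly follow-up study visits for all treatment group participants will be analyzed for quantitative hair drug levels" (SAP 8.5.2). The protocol's text on objective adherence measures lists collection at Months 0, 3, 6, 9 and 12, and accepts "occipital hair >0.5cm in length with absence of bleaching".

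**What hair represents.** SAP 2.2.4 gives "Quantitative amount of doxycycline in 1cm segments from cut end to tip which corresponds with a 4-week period of dPEP use", beginning one week before sampling. Item 2 of 8.5.2, which compares hair with SMS reports, dates the sample as "5 weeks prior to study visit until 1 week prior to study visit".

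**Interim infections.** SAP 2.2.1 gives an example: a new GC infection diagnosed "at an interim visit 40 days after their 6 month visit, this will be analysed as a primary 9 month endpoint". SAP 7.5.1 states the same carry-forward rule in general.

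**Stated justification.** SAP 8.5.2 assumes that women either take dPEP regularly or do not take it, and limits the analysis to use against non-use.

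**The concern.** An exposure meant to explain an infection should be measured over time before that infection. The carry-forward rule suits the primary analysis, where the exposure is the randomised arm and does not change. In 8.5.2 the exposure is measured at the end of the quarter, so an infection found early in the quarter is matched to drug use that came later. What a woman does after a diagnosis and counselling may differ from what she did before it, and the documents give no basis for predicting in which direction.

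A second, milder problem is that item 1 leaves the hair window open. The exposure period could then vary with hair length, and the analyst could choose it after seeing the data.

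If the intention-to-treat result were weak, this analysis would be one of the main aids for telling an ineffective drug from an untaken one. It relates an objective measure of use to infection; the SAP's other adherence measures (calendar and SMS) are self-reported.

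**Working it through.** **Inputs.** Hair window: weeks 5 to 1 before the visit (SAP 8.5.2 item 2). Segment scale: 1 cm per 4 weeks, starting one week back (SAP 2.2.4). Interim example: day 40 after Month 6 (SAP 2.2.1). Quarter length is not given in days; I assume 91 and show 84 as the short end.

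**1. The plan's own figure.** 5 − 1 = 4 weeks = 28 days, which agrees with one 1-cm segment in 2.2.4.

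**2. Position of the window.** With a quarter of Q days, the window is day Q − 35 to day Q − 7.
- Q = 91: days 56 to 84.
- Q = 84: days 49 to 77.

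**3. Day-40 example.** Gap from diagnosis to window opening = Q − 35 − 40.
- Q = 91: 16 days.
- Q = 84: 9 days.

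Any interim diagnosis up to day 56 (day 49 if Q = 84) has its whole window after diagnosis. Acquisition is earlier still.

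**4. Segments against the day-40 diagnosis (Q = 91).**

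| Segment | Days before visit | Day of quarter | Relative to diagnosis |
|---|---|---|---|
| 1 | 7–35 | 56–84 | wholly after |
| 2 | 35–63 | 28–56 | straddles |
| 3 | 63–91 | 0–28 | wholly before |

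**5. Coverage of the quarter.**
- One segment: 28/91 = 31% (28/84 = 33%). The first 56 days (62%) and the last 7 days (8%) are unseen.
- Two segments: 56/91 = 62%. Three: 84/91 = 92%, with no carry-over.
- Hair of 0.5 cm: 14/91 = 15%.
- A fourth segment would add 28 days from the previous quarter.
- If Q = 84, segment 3 reaches 91 − 84 = 7 days behind the previous visit.

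**6. Illustrative attenuation from a one-segment window.** Assumptions: true RR 0.50 and 60% use. Post-diagnosis behaviour is not modelled.

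(a) Use changes once, at a uniform time, in 10%, 20% or 40% of quarters (simulation, quarterly risk without use 6%): RR about 0.52, 0.55, 0.61. With no change there is no bias.

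(b) Monthly on/off model over three months, month-to-month correlation r, risk 1.0 in an unused month and 0.5 in a used one. Classify by the last month. For k months earlier, P(use | last month used) = 0.6 + 0.4r^k and P(use | last month unused) = 0.6(1 − r^k).
- r = 0.5: (0.50 + 0.60 + 0.65)/(1 + 0.85 + 0.775) = 1.75/2.625 = 0.67.
- r = 0.8: (0.50 + 0.54 + 0.572)/(1 + 0.94 + 0.892) = 1.612/2.832 = 0.57.

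**7. Would any detection in segments 1 to 3 repair this?** In model (b), RR = 1 − 0.5 × 0.6/(1 − P0), where P0 = 0.4(0.4 + 0.6r)² is the chance of no use in all three months.
- r = 0.5: P0 = 0.196, RR = 0.63.
- r = 0.8: P0 = 0.310, RR = 0.57.

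So it gains little at r = 0.5 and nothing at r = 0.8; in simulation (a) it gives 0.54, 0.57 and 0.62, slightly worse than one segment. In model (b) risk is linear in the share of months used, so the proportion of segments with drug detected is the matched exposure.

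**The case against.** **All-or-none use.** The SAP assumes regular use or none, and under stable use a one-month window is an adequate proxy for the quarter. This stands, and it limits the coverage point. But the SAP does not say use is constant within a quarter, and the documents provide for change: stopping in pregnancy with later resumption, holds for toxicity with possible reintroduction, and discontinuations longer than two weeks in SAP 7.5.3. Nor does the assumption put the time order right when use changes after a diagnosis.

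**Few events may be affected.** Interim STI testing is done when symptoms are present, and the protocol's background puts the sensitivity of syndromic management below 20%. Most infections may therefore surface at scheduled visits. The share of reversed-order events cannot be derived from the documents. STI treatment avoids doxycycline, so treatment itself should not mark later hair.

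**Stronger readings.** A reader might infer that hair must either cover only the last four weeks or carry over drug from earlier quarters. It need not: two or three segments would cover 62% to 92% of a 91-day quarter without carry-over, and the SAP neither specifies nor excludes that. A reader might also infer that a woman who stopped two quarters ago would count as a user, or that pre-enrolment doxycycline would appear as control-arm contamination in SAP 9.2. Both need a whole-strand reading and long hair. The documents give no participant hair lengths beyond the minimum, and wherever the SAP dates a hair measure it uses about one month.

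**Conclusion.** The time-order fault holds. Under the only hair window the SAP dates, an interim infection diagnosed up to about day 56 of a 91-day quarter is matched to exposure wholly after its diagnosis, and the SAP's own example is such a case, by 16 days (9 if the quarter is 84 days). How many events are affected, and the direction of the resulting bias, are unknown.

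The window in item 1 is undefined. Read as one month, it covers about 31% of the quarter. The attenuation is nil if use is stable, and illustratively moves a true RR of 0.50 to between 0.52 and 0.67 depending on how often use changes. Larger attenuation, such as an RR of 0.79 (1.9/2.4 in the monthly model with r = 0), needs use in one month to say nothing about the next, which is the opposite of what the SAP assumes.

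This is a non-randomised comparison within the dPEP arm. The intention-to-treat analysis and the sample size are untouched.

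**What to change.** Before database lock, add to SAP 8.5.2 items 1 and 3:

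- **Interim infections.** Take exposure only from 1-cm segments lying wholly before the diagnosis date and within that quarter. Set exposure to missing if the hair is too short or no such segment was assayed, and report how many events this removes.
- **Scheduled-visit infections and STI-free quarters.** Use the proximal 1-cm segment for all women as the main version, and state how hair of 0.5 to 1 cm is handled. As a sensitivity analysis, use the proportion of segments 1 to 3 with drug detected, where length allows. Never use segments grown before the previous scheduled visit, and state a tolerance for short quarters, since segment 3 overruns an 84-day quarter by 7 days.
- **SAP 9.2.** State that segments grown before enrolment do not count as contamination.
- **Resolution.** Reconcile the protocol's weekly hair segments with the SAP's 4-week segments.

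The cost is wording and programming, because 1-cm segment values are already planned in 2.2.4. The downside is missing exposure for some interim events. In a 91-day quarter, a diagnosis before day 28 has no usable segment, and one between days 28 and 56 needs about 3 cm of hair. Because only events are dropped, absolute risks would be understated; the ratio is distorted only if the loss is related to use.
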